### 3.2 Secondary Objectives

The secondary objectives are:

- Determine the pharmacokinetic profile of JKB-121 in nonalcoholic steatohepatitis (NASH)
- Assess the impact of treatment with JKB-121 on metabolic markers
- Assess the impact of treatment on liver enzymes (serum alanine aminotransferase [ALT]) over 24 weeks.
- Establish the recommended dose for future NASH treatment studies.
- To evaluate changes of NASH related biomarkers such as adiponectin, leptin, ghrelin, tumor necrosis factor alpha (TNF-alpha), TGF-beta, hyaluronic acid and matrix metalloproteinase 2 (MMP-2).

### 3.3 Exploratory Objective

Investigate the impact of treatment of potentially relevant inflammatory and metabolic biomarkers associated with NASH.

## 4 STUDY OVERVIEW

### 4.1 Study Design

[figure not shown]
This is a randomized, double-blind, placebo controlled, parallel-group, phase II trial of JKB-121 in treating subjects with biopsy-proven NASH.

Subjects will be randomized at study entry to placebo twice daily, 5 mg twice daily, or 10 mg twice daily of JKB-121 orally to improve NASH with regard to biochemical and MRI/MRS features of NASH in a 1:1:1 ratio.

- Treatment Group 1: placebo twice a day orally
- Treatment Group 2: 5mg of JKB-121 twice a day orally
- Treatment Group 3: 10 mg of JKB-121 twice a day orally

The maximum time on study drug for each subject is 24 weeks with an additional 4 weeks of follow-up.

This allocation is shown diagrammatically below:

### 4.2 Randomization and Treatments

Patients will be randomized in the order in which they are enrolled into this double-blind study by using a computer-generated randomization schedule. TaiwanJ Pharmaceuticals prepared the schedule prior to the start of the study. This number will designate which allocated treatment a patient will receive. The randomization schedule will be a ratio of 1:1:1 to one of the following three treatment groups:

- JKB-121 5 mg tablet twice daily orally
- JKB-121 10 mg tablet twice daily orally
- Placebo as tablet twice daily orally

Treatment allocation will be stratified by known diagnosis of diabetes status. Nondiabetic status will be defined as  $HbA1c \leq 6.0$  and absence of any medications to treatment diabetes. Diabetic status will be defined as  $HbA1c > 6.0$  and/or requiring medication for treatment of diabetes mellitus.

Subjects who are withdrawn from the study will not be replaced.

Until formal conclusion of the study, subjects, investigators and all site study personnel will be remain blinded as to treatment allocation, except in the event of a medical emergency which necessitates unblinding.

## 5 EFFICACY ENDPOINTS

### 5.1 Primary Efficacy Endpoint

Mean and absolute changes from baseline in the percentage fat content of the liver measured by magnetic resonance imaging (MRI) at week 24.

### 5.2 Secondary Efficacy Endpoints

- Mean and absolute changes from baseline in the percentage fat content of the liver measured by magnetic resonance imaging (MRI) at week 12.
- Time to remission (TTR) defined as the time in weeks from randomization to liver function remission as defined as two consecutive ALT values within normal range ( $<20$  U/L for women and  $<30$  U/L for men). The time of the first of the two consecutive ALT values within normal range will be used as the TTR.
- Percentage of subjects reaching liver function remission as defined as two consecutive ALT values within normal range ( $<20$  U/L for women and  $<30$  U/L for men).
- Percentage of subjects at each scheduled visit whose ALT level is within normal range ( $<20$  U/L for women and  $<30$  U/L for men).
- Percentage of subjects whose ALT level is within normal range ( $<20$  U/L for women and  $<30$  U/L for men) at any time within the following time intervals which will be derived using actual study days:
  - Baseline to Week 12
  - Week 12 to Week 24
- Percentage of subjects achieving a 20% reduction in ALT from baseline at any time during the study period.
- Change from baseline in serum ALT at each scheduled visit.

- Serum aspartate aminotransferase (AST), ALT, and gamma-glutamyl transpeptidase (GGT) at each scheduled visit and the corresponding changes from baseline.

All endpoints which define the normal range as <20 U/L for women and <30 U/L for men will be repeated with the normal range defined as <40 U/L.

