	
• HbA1c and the homeostatic model assessment of insulin resistance (HOMA-IR)• Serum lipid profile: total cholesterol, triglycerides, low density lipoprotein (LDL) and high density lipoprotein (HDL) fractions. 
Liver Function:
 
• Mean change from baseline in serum ALT at week 24.• Mean serum aspartate aminotransferase (AST), alanine aminotransferase (ALT), and gamma-glutamyl transpeptidase (GGT) at weeks 4, 8, 12, 16, 20, and 24.• Proportion of subjects whose ALT level at week 24 is within normal range defined as < 20 U/L for women and < 30 U/L for men.
Exploratory Outcome Measures:	
• Mean serum concentrations of lipopolysaccharide (LPS), c-reactive protein (CRP), cytokeratin (CK)-18 fragments, proinsulin c-peptide, glucagon-like polypeptide (GLP-1) and adiponectin.• Relative levels of inflammatory cytokines, interferon gamma (IFN-γ), and tumor necrosis factor alpha (TNF-α)• Relative levels of regulatory T cells in the peripheral blood mononuclear cells (PBMC) samples including CD4, CD8, CD 25, Fox P3, NKT, and CD62 T cells.
Methodology:	
Study design	Randomized double blind, placebo control 3-arm parallel group, multi-dose single center study
Study duration	Up to 28 days for screening, 24 weeks of treatment and 28 days of follow-up. Subjects terminating study drug will be followed-up post-treatment for 28 days.
Number of Subjects:	The study will aim to recruit 60 subjects, randomized 1:1:1
Stratification:	Treatment allocation will be stratified by known diagnosis of diabetes status. Nondiabetic status will be defined as HbA1c \leq 6.0 and absence of any medications to treat diabetes. Diabetic status will be defined as HbA1c $>$ 6.0 and/or requiring medication for treatment of diabetes mellitus.
Study Drug:	JKB-121 oral tablet
Control Group	Placebo to match
Dose Regimens	Arm A: 5 mg JKB-121 twice daily. Arm B: 10 mg JKB-121 twice daily Arm C: Matching placebo twice daily All treatment dose regimens are administered per orally
Administration: Schedule:	Twice daily for 24 weeks

Study Population:	Adults with biopsy-proven nonalcoholic steatohepatitis (NASH)

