13.2 General Statistical Methodology

Prior to database lock, a final detailed Statistical Analysis Plan (SAP) will be available. Results, when available, will be summarized into tabulations, case listings, plots, and histograms for comparison.

Three major study populations are planned, modified intent-to-treat (met) population, per protocol (PP), and safety populations.

Baseline variables will be ascertained for conformity among all stratification factors. All baseline analysis will be based on the met population. In the met population, the subjects will be counted in the treatment group to which they were randomized, as long as they received at least one dose of study medication and have at least one return visit.

The safety analysis will be based on the safety population. In the safety population, subjects will be counted in the group in which they were treated. To assess the robustness of the study outcomes, a sensitivity analysis will be performed on all pertinent major efficacy variables. The sensitivity analysis will include and exclude patients with major study deviations and early withdrawals to assess the impact on the study endpoints.

The criteria may be amended prior to unbinding of the treatment assignment for the analysis of data. Reasons for changes may include study conduct changes, protocol amendments, or changes in the appropriateness of the criteria, which may be assessed based on review of blinded data.

For all analyses, all missing values due to patient early termination from the study will be not imputed.

For each patient, the Baseline values will be defined as those values recorded at Day 1 prior to dosing or Screening, as appropriate.

All hypotheses will be tested for statistical significance with two-tailed p-values. Results of all tests will be considered statistically significant if their p-value is less than or equal to 0.05, except for results of the tests for interaction will be considered statistically significant if the p-value is less than or equal to 0.10.

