### 6.9.2.2 Liver Function

The same descriptive statistics, ANCOVA model, and multiple imputation as the primary efficacy endpoint will be applied to serum aspartate aminotransferase (AST), ALT, and gamma-glutamyl transpeptidase (GGT) at each scheduled visit for the Full Analysis Set Population and the mITT Population.

As a sensitivity analysis, the change from baseline in AST, ALT, and GGT will be analyzed using a mixed-model repeated-measures (MMRM) ANCOVA model for the Full Analysis Set Population, implemented using SAS® Proc Mixed. The factors in the model will be diabetes stratum, treatment group, baseline value, visit, and the treatment group by visit interactions. An unstructured covariance matrix will be used (TYPE=UN). No imputation will be performed. The sample SAS code can be found below:

```
*****
Note:
  USUBJID = unique subject identifier
  TREATMENT = 0, (placebo), 1 (JKB-121 5 mg), 2 (JKB-121 10 mg)
  DIABSTAT = nondiabetic, diabetic
  VISIT = visit
  BASE = baseline value
  CHG = change from baseline to the specified visit
*****;
proc mixed;
  class USUBJID DIABSTAT TREATMENT BASE VISIT;
  model CHG = DIABSTAT TREATMENT BASE VISIT TREATMENT*VISIT;
  Repeated VISIT / TYPE=UN sub=USUBJID;
  lsmeans VISIT*TREATMENT / cl pdiff slice=VISIT;
run;
```

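### SAP 5.2 does not single out Week 24 for ALT as the protocol synopsis does, so unranked tests at every visit give an inactive drug about a 20–50% chance of at least one p ≤ 0.05

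*SAP*

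**What the plan says.** The Liver Function list in the protocol synopsis gives a time point to two ALT endpoints: "Mean change from baseline in serum ALT at week 24" and "Proportion of subjects whose ALT level at week 24 is within normal range", with normal defined as below 20 U/L for women and below 30 U/L for men. The same list also makes mean AST, ALT and "gamma-glutamyl transpeptidase (GGT) at weeks 4, 8, 12, 16, 20, and 24" secondary, without ranking them. Elsewhere the protocol is looser. Section 5.2.2 speaks of ALT change over the 24 weeks, section 13.4.1.2 names no visit, and 5.2.2 calls time to remission the secondary endpoint of the study.

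SAP 5.2 lists "Change from baseline in serum ALT at each scheduled visit" and, likewise by visit, the percentage with normal ALT. It adds: "All endpoints which define the normal range as <20 U/L for women and <30 U/L for men will be repeated", this time with a limit of 40 U/L.

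SAP 6.9.2.2 applies the primary ANCOVA to AST, ALT and "gamma-glutamyl transpeptidase (GGT) at each scheduled visit for the Full Analysis Set Population and the mITT Population". That model (SAP 6.9.1) compares each dose with placebo, reports two-sided p-values and makes no multiplicity adjustment. Protocol 13.2 states: "All hypotheses will be tested for statistical significance with two-tailed p-values", and then: "Results of all tests will be considered statistically significant if their p-value is less than or equal to 0.05", with a separate limit for interaction tests only.

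**The concern.** For liver fat, the SAP does rank its time points: Week 24 is primary and Week 12 secondary. ALT gets no ranking, although it is the only secondary outcome with a stated power and that power is for a single 30 U/L effect. A reader of the results would have no prespecified ALT visit to look at first. An isolated p ≤ 0.05 at, say, Week 8 could be presented as the ALT finding, while a null result at Week 24 would carry no more weight than any other visit.

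Week 28 counts too. SAP 6.9.2.1 confines time to remission and the responder analyses to the treatment period, but 6.9.2.2 has no such limit, and Protocol 10.4.5 draws ALT at the off-drug follow-up visit.

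Choosing a dose for later NASH studies is a secondary objective in both documents, and neither gives a rule for that choice, so a stray ALT result could be given weight in it.

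**Working it through.** **The plan's own figure.** The documents state no error rate for a family of tests. Their only ALT figure is 73% power (SAP 6.1: 20 per arm, difference 30 U/L, SD 50, two-sided 0.05, unpaired t-test).
- SD of change = √(40² + 40² − 2 × 0.25 × 40 × 40) = √2400 = 49.0, which the plan takes as 50.
- Standard error of the difference = 50 × √(2/20) = 15.8, and 30/15.8 = 1.90.
- Power is 47.5% by the normal approximation and 45.6% by the t-test.

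The 73% therefore does not reproduce. That is a separate matter and does not enter the results below.

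**Inputs from the documents**
- Two-sided 0.05 per test (Protocol 13.2).
- Two dose-versus-placebo comparisons per visit, unadjusted (SAP 6.9.1).
- 20 per arm (SAP 6.1).
- ALT drawn at Weeks 2, 4, 8, 12, 16, 20, 24 and 28 (Protocol 10.2.1 and 10.4). This gives 7 × 2 = 14 on-treatment tests, or 16 with Week 28. The protocol synopsis list of six visits gives 12.

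**Assumption.** The documents do not give the correlation of ALT between post-baseline visits. The range used is 0.25 to 0.9. The plan's 0.25 is a pre/post correlation, so it is used for baseline and is only a guess for between visits.

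**Upper reference, independent tests:** 1 − 0.95^k gives 0.46 for 12 tests, 0.51 for 14 and 0.56 for 16.

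**Simulation of the SAP's ANCOVA** (treatment, diabetes stratum, baseline) with no drug effect, complete data and a shared placebo arm; 6,000 trials per case, so the simulation error is at most about 0.006. Correlation with baseline is held at 0.25. Each cell gives the chance of at least one p ≤ 0.05 in either direction, then in the favourable direction only.

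| Visits | ρ = 0.25 | ρ = 0.5 | ρ = 0.7 | ρ = 0.9 |
|---|---|---|---|---|
| 6 (protocol list) | 0.405 / 0.212 | 0.366 / 0.183 | 0.291 / 0.145 | 0.190 / 0.094 |
| 7 (on treatment) | 0.462 / 0.245 | 0.397 / 0.201 | 0.320 / 0.162 | 0.202 / 0.100 |
| 8 (with Week 28) | 0.501 / 0.268 | 0.427 / 0.219 | 0.340 / 0.172 | 0.212 / 0.109 |

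Week 24 alone with two doses gives about 0.09, or about 0.045 favourable. This is a little under 1 − 0.95² = 0.0975 because the doses share a placebo arm.

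**Checks**
- If the correlation with baseline rises along with ρ, the fall at high ρ largely disappears: at ρ = 0.9 the chance is 0.398 for 7 visits and 0.420 for 8. After baseline adjustment, the correlation between visits is (ρ − r²)/(1 − r²), where r is the correlation with baseline. With ρ = 0.9 this is 0.89 for r = 0.25 but only 0.47 for r = 0.9.
- If correlation decays with time (0.5 to 0.9 per four weeks), 7 visits give 0.435 to 0.336 and 8 visits give 0.476 to 0.358.
- A separate normal-theory simulation (200,000 trials per case, 8 visits) gives 0.497, 0.411, 0.296 and 0.208 at ρ = 0.25, 0.5, 0.75 and 0.9.

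The count covers ALT change in one population only. It leaves out AST, GGT, the mITT repeat, the repeated-measures contrasts and the responder tests under two normal ranges.

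**The case against.** The strongest reply is that the protocol is itself unranked. The list that names Week 24 also makes six visits secondary, and testing those gives about 19–41%. Sections 5.2.2 and 13.4.1.2 name no visit, and the secondary endpoint the protocol singles out is time to remission. This stands. What the SAP adds is Weeks 2 and 28 and the loss of the Week 24 label. A reader might infer that the SAP replaced the Week 24 endpoint and so raised the risk from 9% to 50%. The documents do not support that: Week 24 is still tested, and most of the multiplicity was already in the protocol.

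Second, SAP 6.1 calls the objectives exploratory and waives adjustment for the co-primary endpoints and for comparisons among the three arms. A reader might infer a breached error rate, but 0.05 is a threshold for each test and no family-wise rate is promised. This also stands. The stated waivers do not mention visits, however, and an exploratory aim does not remove the use of saying in advance which visit is read first.

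Third, the upper figure needs low correlation and the off-drug visit, and it counts apparent harm as well as benefit. That is correct, and the favourable-direction figures are the ones that bear on a false claim of activity.

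Fourth, the 40 U/L repeat is not simply extra testing, because Protocol 13.4.1.2 defines remission that way. This stands, and it is a reason to reconcile the definitions.

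**Conclusion.** The point holds as a gap in ranking. The SAP does not carry over the synopsis's Week 24 time point for ALT change and ALT normalisation, and it tests ALT change at every visit for two doses with nothing ranked first. For an inactive drug, the chance of at least one p ≤ 0.05 for ALT change over the 14 to 16 tests is about 20–50% in either direction and about 10–27% in the favourable direction, against about 9% and 4.5% at Week 24 alone. These figures rest on an assumed between-visit correlation of 0.25–0.9 and on complete data. The consequence is a risk of selective reading in an openly exploratory trial. It does not invalidate the planned analyses, and it is worth correcting because the correction is cheap.

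**What to change.** Change the SAP only:
- In 5.2 and 6.9.2.2, name Week 24 as the time point for ALT change from baseline, with each dose compared with placebo in the Full Analysis Set.
- In 5.2, with a matching line in the responder text of 6.9.2.1, name Week 24 for the proportion with normal ALT under the <20/<30 U/L definition, as in the protocol synopsis.
- State that ALT at other visits (including off-drug Week 28), AST and GGT are supportive, and are reported with estimates, 95% confidence intervals and p-values labelled nominal.
- Keep time to remission as the secondary endpoint that the protocol names. Reconcile the 40 U/L repeat with the conflicting remission definitions in Protocol 5.2.2 (<20/<30 U/L, or a 20% reduction) and 13.4.1.2 (<40).

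No table is dropped and no new data are needed. With both doses tested at Week 24, about 9% remains, in line with the plan's stated choice not to adjust between arms. The cost is that an isolated p ≤ 0.05 at another visit or in another enzyme can no longer be reported as a significant finding.

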### 5.3 Other Efficacy Endpoints

- Metabolic Marker Endpoints
  - Body mass index (BMI) at each scheduled visit and the corresponding changes from baseline.
  - HbA1c and the homeostatic model assessment of insulin resistance (HOMA-IR) at each scheduled visit and the corresponding changes from baseline.
  - Serum lipid profile (total cholesterol, triglycerides, low density lipoprotein [LDL], and high density lipoprotein [HDL]) at each scheduled visit and the corresponding changes from baseline.
- Biomarker Endpoints
  - Biomarkers such as adiponectin, leptin, ghrelin, TNF-alpha, TGF-beta, hyaluronic acid and MMP-2 at each scheduled visit and the corresponding changes from baseline.
- Exploratory Outcome Measures
  - Mean serum concentrations of lipopolysaccharide (LPS), c-reactive protein (CRP), cytokeratin (CK)-18 fragments, proinsulin c-peptide, glucagon-like polypeptide (GLP-1) and adiponectin.
  - Relative levels of inflammatory cytokines, interferon gamma (IFN- $\gamma$ ), and TNF-alpha
  - Relative levels of regulatory T cells in the peripheral blood mononuclear cells (PBMC) samples including CD4, CD8, CD 25, Fox P3, NKT, and CD62 T cells.

## 6 STATISTICAL METHODOLOGY

### 6.1 Sample Size Determination

An approximate total of 60 subjects will be enrolled. Subjects will be randomized into three treatment groups in a ratio of Group 1 (5 mg twice daily): Group 2 (10 mg twice daily): Group 3 (placebo twice daily) = 1:1:1. No empirical power calculation is performed. The sample size is based on the best medical judgment.

The power to detect a difference between placebo and active treatment with respect to change from baseline in liver fat content and serum ALT has been determined for a sample size of 20 patients per arm to assess safety and potential efficacy. Fat quantification by MRI is very sensitive with as small as a 5% detectable change in fat quantification.

Further, since the endpoint is the change from baseline, plausible estimates of the degree of correlation between pre-and post-baseline measurements will be incorporated into the variance estimates. Given the wide range of results observed in the literature, several “what-if” scenarios were examined. As such, the current sample size was considered sufficient for the exploratory objectives of the study for the given range of plausible treatment effects and variance estimates. Due to the exploratory objects of the protocol, no adjustment for the two co-primary endpoints was made. Additionally, there will be no adjustments for multiple comparisons between the 3 treatment groups.

Assuming the observed difference between two treatment groups is 20%, then the 95% confidence interval for the true mean is given by (2.5%, 37.5%) with 20 subjects in each group.

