13. STATISTICAL CONSIDERATIONS

13.1 Sample Size Calculation

The study will need to screen approximately 100 subjects to enroll 60 patients with biopsy-proven NAFLD who meet the study inclusion / exclusion criteria. With 20 subjects per treatment group, the study will not be powered for efficacy assessment between the two doses. Based on precision analysis, the proposed sample size will provide the maximum error (defined as the half-way of the width of the 95% confidence interval for the difference (change in liver-biochemistry) between two doses (5 mg twice daily vs 10 mg twice daily dose) allowed.

Presuming the observed difference between two treatment groups is 20%, then the 95% confidence interval for the true mean is given by (2.5%, 37.5%) with 20 subjects in each group.

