#### ALT change from Baseline:

The current sample size of 20 subjects per group should yield approximately 73% power to detect a treatment effect of at least 30 U/L assuming a SE of 50 U/L ( $\alpha= 0.05$ ; two tailed; unpaired t-test). The SD of 50 U/L for the change from baseline endpoint was derived assuming SDs of 40 for the pre-and post-baseline measurements with a correlation of 0.25.

Sample size and power estimates have not been adjusted for multiple comparisons or multiple endpoints, dropouts or stratifications.

The analysis of each primary endpoint will be based on a linear model that incorporates the baseline measures as a covariate, the stratification factor and randomization treatment group. Pairwise comparisons of each active treatment group to control will be conducted vial linear contrasts.

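### The 95% interval of (2.5%, 37.5%) given for a 20% difference between two groups of 20 matches a one-group formula and cannot be derived as a between-group interval from the stated inputs

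*SAP*

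**What the plan says.** SAP 6.1 (Sample Size Determination) states: "Assuming the observed difference between two treatment groups is 20%, then the 95% confidence interval for the true mean is given by (2.5%, 37.5" percent), "with 20 subjects in each group". The Protocol synopsis carries the same sentence, and Protocol 13.1 repeats it with one word changed: "Presuming the observed difference between two treatment groups is 20%, then the 95% confidence interval for the true mean is given by (2.5%, 37.5" percent).

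Protocol 13.1 introduces the figure as a matter of precision rather than power: "Based on precision analysis, the proposed sample size will provide the maximum error". It defines that error as the "half-way of the width of the 95% confidence interval for the difference (change in liver-biochemistry) between two doses", meaning 5 mg versus 10 mg twice daily.

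None of the three places says whether 20% is a difference in proportions or in mean percentage change. None gives a rate for either group, an SD on a percentage scale, or a formula. The only SDs in the sample-size text are for ALT in U/L: "SDs of 40 for the pre-and post-baseline measurements with a correlation of 0.25", leading to 50 U/L for the change. They are not linked to this interval.

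**The concern.** The sentence is about a difference between two groups, yet its interval is for a true mean. No variance for a second group is visible in the result. A one-group formula gives both printed limits from the three stated numbers alone (20%, 20 subjects, 95%).

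The figure matters because Protocol 13.1 says the trial is not powered to compare the two doses and relies on precision instead. This is the only computed precision figure in that section. Choosing a dose for later studies is a secondary objective (Protocol 5.1.2). A reader would take from it that an observed 20% difference comes with a margin of 17.5 points and an interval clear of zero. Nothing in the documents supports that for two groups of 20.

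**Working it through.** **Inputs.** Observed difference 20%, printed interval (2.5%, 37.5%) and so a half-width of 17.5 points, and 20 per group (SAP 6.1). Allocation: "Group 3 (placebo twice daily) = 1:1:1". Two-sided 95%, so z = 1.96 (Protocol 13.2: "All hypotheses will be tested for statistical significance with two-tailed p-values"). ALT: SD 40 U/L before and after, correlation 0.25, SD of change 50 U/L (SAP 6.1, ALT paragraph). The rates or percentage-scale SD behind the interval are not stated, so ranges are shown below as assumptions.

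**Step 1. Reproduce the printed figure.** One group, Wald interval:

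1.96 × √(0.20 × 0.80 / 20) = 1.96 × 0.0894 = 0.1753, giving (2.47%, 37.53%).

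This agrees with the printed limits to rounding. Other one-group intervals do not: a t(19) multiplier gives a half-width of 18.7 points, Wilson gives (8.1%, 41.6%) and Clopper-Pearson (5.7%, 43.7%).

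**Step 2. Read 20% as a difference in proportions.** Half-width = 1.96 × √[(p₁q₁ + p₂q₂) / 20], where q = 1 − p.

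| Assumed rates | Half-width (points) | 95% interval |
|---|---|---|
| 0% vs 20% | 17.5 | (2.5%, 37.5%) |
| 5% vs 25% | 21.2 | (−1.2%, 41.2%) |
| 10% vs 30% | 24.0 | (−4.0%, 44.0%) |
| 20% vs 40% | 27.7 | (−7.7%, 47.7%) |
| 40% vs 60% | 30.4 | (−10.4%, 50.4%) |

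By symmetry, 80% vs 100% gives the same result as 0% vs 20%. The half-width for a 20-point difference is largest at 40% vs 60%. Zero enters the interval once the lower rate exceeds about 3.1% (mirror case: once the higher rate falls below about 97%). With 20 per group, observed rates move in steps of 5%, so a 20-point difference means four responders. There are 17 such pairs of counts, from 0 vs 4 to 16 vs 20. Only the first and last give the printed interval; the other 15 include zero.

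**Step 3. Read 20% as a difference in mean percentage change.** Half-width = multiplier × SD × √(2/20). Solving for a half-width of 17.5:

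- t(38): 17.5 / (2.024 × 0.3162) = 27.3 points
- z: 17.5 / (1.96 × 0.3162) = 28.2 points

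An SD of 27 to 28 points would therefore make the printed interval correct. Zero would enter only if the SD exceeded about 31 (t) or 32 (z) points.

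**Step 4. What the plan's own SDs give.** For the difference in mean ALT change:

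- Unadjusted: 2.024 × 50 × √(2/20) = 32.0 U/L.
- Baseline-adjusted: residual SD = 40 × √(1 − 0.25²) = 38.7 U/L, so 2.024 × 38.7 × 0.3162 = 24.8 U/L.

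These are in U/L. Turning them into percentages needs a mean ALT, which the documents do not give.

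**The case against.** The best defence is that no document calls the 20% a proportion. Protocol 13.1 speaks of a change in liver biochemistry, and all three places refer to a mean. On a continuous reading, an SD of 27 to 28 points gives exactly the printed interval for two groups. The plan's ALT SD does not rule this out. A half-width of 32.0 U/L equals 17.5% of a mean ALT of about 183 U/L (32.0 / 0.175), and 24.8 U/L equals 17.5% of about 142 U/L. Both means lie within the range that eligibility allows, from above 40 U/L (women) or 60 U/L (men) up to 250 U/L (Protocol 8.1 and 8.2). This stands: a reader might infer that the interval is certainly a one-group interval, and the documents do not prove it. They leave the needed SD unstated, so the figure is unsupported rather than shown to be false.

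A second defence is that 0% versus 20% is a legitimate two-group case. Remission requires two consecutive ALT values below 20 or 30 U/L in patients who enter above 40 or 60 U/L, so a placebo rate near zero is possible. This also stands as a possibility. But no document assumes it, and Protocol 13.1 applies the interval to two active doses, one of which would need no responders (or the other all responders).

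Third, the sample size is said to rest on medical judgment, separate power statements exist for liver fat and ALT, and no analysis uses this interval. That is correct, and it limits the consequence to the stated precision.

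**Conclusion.** The point holds in this form: the printed interval matches a one-group Wald calculation, and it cannot be derived as a between-group interval from what the documents state. The readings that would rescue it need an unstated input, either 0% versus 20% (or 80% versus 100%), or a percentage-scale SD of about 27 to 28 points.

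On the proportion reading, the half-width is understated by about 4 points (21.2 − 17.5 = 3.7) at 5% versus 25%, and by about 13 points (30.4 − 17.5 = 12.9) at 40% versus 60%. A reader might go further and conclude that the plan wrongly excludes zero. That follows only if 20% is a difference in proportions and the lower rate is above about 3% (or, in the mirror case, the higher rate is below about 97%). It does not follow on the continuous reading. Nor do the documents support the inference that 60 subjects is the wrong number because of this sentence.

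The importance is moderate. All figures assume 20 evaluable subjects per group; SAP 6.1 makes no allowance for dropout, and losses would widen every interval.

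**What to change.** In the Protocol synopsis, Protocol 13.1 and SAP 6.1, replace the sentence with a two-group interval on a named endpoint that uses both groups' variances, and state the formula and inputs.

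One option uses only the plan's own inputs: *With 20 subjects per group, the half-width of the 95% confidence interval for the difference in mean ALT change is about 32 U/L (SD 50 U/L), or about 25 U/L with baseline adjustment (SD 40 U/L, correlation 0.25).*

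If a proportion is meant, name the responder definition, state the assumed rate in each group and give the resulting half-width: about 21 to 30 points for rates from 5% versus 25% to 40% versus 60%. If a mean percentage change is meant, state its SD and where it comes from.

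In each place, make the interval one for the true difference rather than for the true mean. In Protocol 13.1, give the maximum error as the recomputed half-width, which is how that section already defines it.

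The cost is wording in three places. If a proportion is meant, the stated precision becomes less favourable unless one of the two extreme cases is assumed and justified. No further patients are needed, and no endpoint, test or analysis changes.
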